#### 1. INTRODUCTION AND OBJECTIVES OF ANALYSIS

#### 1.1. Introduction

Hyperphosphataemia (HP) is a common and serious complication in subjects with chronic kidney disease (CKD), particularly those with end-stage renal disease (ESRD) requiring dialysis. In the paediatric population, CKD is most commonly caused by congenital anomalies of the kidney and urinary tract such as aplasia/hypoplasia/dysplasia and obstructive uropathy. The frequency of such conditions is low. Glomerular diseases of various aetiologies, (e.g., polycystic kidneys, pyelonephritis) can also cause CKD, but with a lower frequency. HP plays an important role in the pathophysiology of major CKD complications for example secondary hyperparathyroidism, renal bone disease and cardiovascular disease, and appears to promote the progression of CKD towards ESRD. High levels of serum phosphorus are considered to be a risk factor for mortality, morbidity and hospitalisation in patients with ESRD.

Complications most relevant to the paediatric population are renal bone disease, also called renal osteodystrophy (sometimes referred to as mineral bone disease), cardiovascular disease and growth failure.

As the efficacy and safety of PA21 has been confirmed in adult subjects with CKD on dialysis, the aim of this Phase 3 clinical study is to demonstrate similar efficacy of PA21 in paediatric and adolescent subjects with CKD, and to provide safety and dosing information for this subject population. The Phoslyra group provides information for a descriptive comparison of PA21 against a commonly used calcium-based phosphate binder (calcium acetate).

This Statistical Analysis Plan (SAP) has been developed for the final analyses of protocol PA-CL-PED-01 (Version 2.0, 22 September 2015), prior to final database lock. It outlines the efficacy and safety analyses, including tables, listings, and graphical presentations to be included in the Clinical Study Report (CSR). A complete draft SAP has been developed and approved by the sponsor statistician before any significant accumulation of data.

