- with any treatment-emergent adverse events by intensity assessed by investigator (mild, moderate, severe),
- with any treatment-emergent adverse events by age at randomisation (0-<2, 2-<6, 6-<12, 12-<=18). The denominator will be the number of patients in each age group category,
- with any treatment-emergent adverse event of special interest (listed in Table 8 below),
- with any serious treatment-emergent adverse event,
- with any serious treatment-related treatment-emergent adverse event,
- with any serious treatment-emergent adverse event that led to death,
- with any non-serious treatment-emergent adverse event,
- with any treatment-emergent adverse events that led to study drug discontinuation,
- and with any treatment-emergent adverse events started <4 weeks (<1 weeks, 1-<2 weeks and 2-<4 weeks will also be presented for more granularity), 4 to <12 weeks, 12 to <24 weeks, ≥24 weeks. The denominator is the number of patients at risk at the beginning of

the period (excluding those who have withdrawn or completed); i.e. in the category 2-<4 weeks, the denominator will include patients at risk/active at week 2.

Related events include Events with Certain or Probably/Likely or Possible as causality assessed by the investigator. Unrelated events include unlikely or unrelated as causality assessed by the investigator.

 Table 8
 Adverse Event of special interest definition

Events of special interest	MedDRA
Diarrhoea	MedDRA PT: -Diarrhoea
Potential of iron accumulation	MedDRA PT: -Cardiac iron overload -Haemochromatosis -Haemosiderosis -Hereditary haemochromatosis -Hepatic siderosis -Iron overload -Pulmonary haemosiderosis -Superficial siderosis of central nervous system
Masking of GI bleeding due to discoloured stool	MedDRA PT: -Faeces discoloured MedDRA SMQs: -SMQ GI haemorrhage
Events, which could be linked to (deficiencies in) growth and skeletal development and review of bone markers	SOC: Musculoskeletal and connective tissue disorder -HLT: Bone disorders NEC (from HLGT Bone disorders (excl congenital and fractures)) -HLT: Metabolic bone disorders NEC (from HLGT Bone disorders (excl congenital and fractures)) -HLGT: Fractures  SOC: Metabolism and nutrition disorders -HLT: Bone metabolism disorders (HLGT: Bone, calcium, magnesium and phosphorus metabolism disorders) -HLT: Calcium metabolism disorders (HLGT: Bone, calcium, magnesium and phosphorus metabolism disorders)

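### The special-interest group labelled as covering growth is defined only by bone, fracture and calcium term levels, so growth events may be absent from the special-interest outputs

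*SAP*

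**What the plan says.** Table 8 in SAP section 4.9.1 defines four groups of adverse events of special interest. The fourth is labelled "Events, which could be linked to (deficiencies in) growth and skeletal development and review of bone markers". Its definition names two system organ classes, musculoskeletal and metabolic, and lists five MedDRA levels under them. It gives no individual preferred terms.

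Table 8 is the operating definition, not an illustration. Section 4.9.1 calls for tables by system organ class and preferred term of subjects "with any treatment-emergent adverse event of special interest (listed in Table 8 below", repeats the adverse event overview for the same events, and adds a by-subject listing. In section 7 these are Tables 14.3.1.3 and 14.3.1.4 (overview), Tables 14.3.1.20 and 14.3.1.21 (by class and term) and Listing 16.2.7.6.

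Section 1.1 names the complications that matter most in children: renal bone disease, then "cardiovascular disease and growth failure". Growth failure stands there as its own item, apart from bone disease.

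**The concern.** The label promises two things, growth and skeletal development, and the listed levels appear to deliver only the second. A programmer who follows Table 8 literally would retrieve bone, fracture and calcium events. An investigator's report of, say, growth retardation or failure to thrive would not be picked up unless the dictionary files it under one of the five levels.

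What is at stake is how the special-interest outputs are read. If they show no growth event, a reader of the study report cannot tell whether none occurred or none was searched for. The plan itself names growth failure as a main paediatric complication, and treatment can last up to 10 + 24 = 34 weeks (Stage 1 plus Stage 2, section 2.1), so this reader will want a clear answer.

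**Working it through.** There is no figure in the plan to reproduce. The check compares the row's label with its definition and then follows a growth event through the planned outputs.

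**Step 1: the five levels, from Table 8.**

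| Level as listed | Subject, by its name | Names growth? |
|---|---|---|
| "SOC: Musculoskeletal and connective tissue disorder -HLT: Bone disorders NEC" | bone | no |
| "HLT: Metabolic bone disorders NEC (from HLGT Bone disorders (excl congenital and fractures" | bone | no |
| "HLGT: Fractures" | fracture | no |
| "HLT: Bone metabolism disorders (HLGT: Bone, calcium, magnesium and phosphorus metabolism disorders" | bone | no |
| "HLT: Calcium metabolism disorders (HLGT: Bone, calcium, magnesium and phosphorus metabolism disorders" | calcium | no |

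The count is 3 bone + 1 fracture + 1 calcium = 5 levels, of which 0 name growth, height, weight gain or thriving.

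**Step 2: is growth added elsewhere?** No other section of the SAP supplements Table 8 with growth terms or defines a second search for them.

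**Step 3: could the bone levels be meant to include growth?** The SAP's own usage speaks against it. The row label gives growth and skeletal development as two subjects, and section 1.1 separates growth failure from renal bone disease. This does not settle the matter, because the SAP does not reproduce the MedDRA hierarchy and one level (bone disorders not elsewhere classified) is a residual group whose content cannot be read from its name.

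**Step 4: a treatment-emergent growth event followed through the outputs**, on the assumption that it lies outside the five levels.

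| Output | Would the event appear? |
|---|---|
| Special-interest overview, Tables 14.3.1.3 and 14.3.1.4 | no |
| Special-interest events by class and term, Tables 14.3.1.20 and 14.3.1.21 | no |
| Special-interest listing, Listing 16.2.7.6 | no |
| All treatment-emergent events by class and term, Tables 14.3.1.6 and 14.3.1.7 | yes |
| The same by age group, Tables 14.3.1.30 and 14.3.1.31 | yes |
| All adverse events, Listing 16.2.7.1 | yes |

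Separately from adverse events, section 4.9.4 summarises height, weight and BMI at each time point by treatment group and by age category (Tables 14.4.9.1 and 14.4.9.2).

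The gap is thus limited to the four special-interest tables and the one special-interest listing.

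**The case against.** The strongest reply has three parts.

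First, the decisive fact lies in the dictionary, which the SAP does not show. Growth terms might sit under one of the five levels. This stands: the text establishes a mismatch between label and level names, and the omission itself is conditional until someone looks it up.

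Second, the event is not lost. It is tabulated with all other treatment-emergent events, overall and by age group, and listed by subject. This also stands. A reader might infer from Table 8 that growth failure would go uncounted altogether; the general tables and Listing 16.2.7.1 rule that out. What they do not provide is the grouping. They show single preferred terms, so the special-interest total would still leave out a child whose only relevant event was a growth event.

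Third, growth is measured directly. Height and weight are scheduled at screening, baseline and Weeks 4, 10, 14, 22 and 34 (Table 2), summarised in section 4.9.4, and bone markers are tabulated in Table 14.4.7.8. So the special-interest search is not the plan's only view of growth, and the SAP does not support the idea that a growth signal would go unseen. The vital-sign summaries are, however, group statistics of actual values and changes. They do not repair a special-interest row that claims to cover growth events.

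It can be added that these tables are descriptive: section 4.9.1 excludes formal testing of adverse event rates, and no population or decision rule depends on Table 8. That limits the weight of the point but does not remove it.

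**Conclusion.** The point holds in a limited form. The fourth row of Table 8 is labelled as covering deficiencies in growth, and 0 of its 5 defining levels name growth. If growth terms are not filed under those levels, a growth-failure adverse event would be absent from Tables 14.3.1.3, 14.3.1.4, 14.3.1.20 and 14.3.1.21 and from Listing 16.2.7.6, while remaining in the general adverse event tables and the listing of all events.

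The conclusion about omission rests on one assumption, inferred from level names: that the five levels contain no growth terms. The label mismatch does not depend on it.

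Two further inferences are not supported. One is a number of children affected: the SAP gives no incidence of growth events, so any such figure would only reflect the rate chosen for it. The other is that the iron row of Table 8 has the same fault because it lists diagnoses and no laboratory terms. A list of accumulation diagnoses fits that row's label, iron laboratory results are summarised separately (Table 14.4.7.6), and section 5 states that transferrin saturation will not be presented.

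**What to change.** Before database lock, look up the five levels of the fourth row in the MedDRA version actually used for coding (section 4.2.2 allows 19.1 or later). Add to that row, as explicit preferred terms, those for impaired growth that the levels do not already contain, for example growth retardation, body height below normal, failure to thrive and poor weight gain, under the names that version uses. Produce the four special-interest tables and the listing from the completed row. If the look-up shows that the levels already contain these terms, a note under Table 8 saying so is enough.

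The cost is one dictionary check and a few added terms, with no new data collection. The downside is that special-interest counts may rise slightly and include events that reflect the underlying kidney disease rather than the study drug.

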#### 4.9.2. Secondary Safety Endpoints

For serum total corrected calcium and serum total corrected calcium-phosphorus product expressed in mmol/L and mmol/L respectively, absolute value and change from baseline value

based on both central and local laboratory data, separately, will be described at each time point by treatment group.

For serum intact parathyroid hormone (iPTH) levels, absolute value and change from baseline value based on central laboratory data will be described at each time point by treatment group and will be expressed in both pmol/L and ng/mL units.

Percentage of subjects who develop at least 1 episode of sustained hypercalcaemia (defined as total calcium value>upper safety limit from Table 6 confirmed by repeat sample 1 week later) after start of treatment will be provided by treatment group. All the records from the local and central laboratories including scheduled and unscheduled visits will be taken into account. Patient will be considered as having an episode of sustained hypercalcaemia if two consecutive assessments separated by 6 days or more have calcium value greater than the upper limit of safety.

#### 4.9.3. Laboratory Data

Clinical laboratory values will be expressed using SI units.

The actual value and change from baseline will be summarised for each clinical laboratory parameter at each time point by treatment group based on central laboratory measurements. For serum phosphorus, calcium (total and corrected) and albumin chemistry parameters, both central and local laboratory summary tables will be provided.

Shift tables from baseline to each post-baseline visit will be produced using the low/normal/high classification based on laboratory reference ranges.

The normal ranges of some parameters from the central laboratory data are only available for the age group above or equal to 18 years and not from 0 to 17yrs; therefore shift tables will not produce for the below parameters due to missing normal ranges. Only Actual Values and Changes Over Time tables and listings will be presented.

- Ferritin
- Osteocalcin
- Transferrin
- Vitamin A
- Vitamin E
- Vitamin K
- Intact parathyroid hormone
- Fibroblast growth factor 23
- Tartrate-resistant acid phosphatase 5b
- Atypical lymphocytes and Lymphocytes atypical/leukocytes

All laboratory data will be provided in data listings.

A subset listing will be presented for all abnormal laboratory values.

**Table 10** List of Laboratory Parameters

Category	Parameters
Haematology	Erythrocytes, Mean corpuscular volume, Mean corpuscular haemoglobin
	Mean corpuscular haemoglobin concentration, Haemoglobin, Haematocrit
	Reticulocyte count, White blood cells, White blood cell differential (% and absolute value), Neutrophils, Eosinophils, Basophils, Lymphocytes, Monocytes, Platelets
Chemistry	Calcium (total, corrected), Intact parathyroid hormone (only shift tables as already summarised as part of the secondary safety endpoints), Creatinine, Glucose, Triglycerides, Total protein, Albumin, Urea, Uric acid, Total bilirubin, Total cholesterol (differential in high density lipoproteins and low density lipoproteins), Creatine phosphokinase, C-reactive protein, Bicarbonate, Sodium, Potassium, Chloride
Chemistry – Liver Enzymes	Alkaline phosphatase, Aspartate transaminase, Alanine transaminase, Lactate dehydrogenase, Gamma-glutamyl transpeptidase
Iron Status Parameters	Iron, Ferritin, Transferrin, Unsaturated Iron Binding Capacity, Transferrin saturation
Vitamins	A, 25(OH)D, 1,25(OH)2D, E, K
Bone Markers	Carboxyterminal cross-linking telopeptide of bone collagen,
	Tartrate-resistant acid phosphatase 5b, Bone-specific alkaline phosphatase,
	Osteocalcin, Fibroblast growth factor 23

In addition, the actual value will be summarised for eGFR (estimated Glomerular Filtration Rate) at each time point by treatment group based on central laboratory measurements for subjects not on dialysis at screening. For subjects not on dialysis at screening but requiring dialysis for the first time during the study, only eGFR values before dialysis will be part of the summary table.

All eGFR values will be listed and for subjects on dialysis, values of glomerular filtration rate will not be deemed interpretable and therefore will be flagged. For subjects on dialysis at screening, all eGFR values will be flagged. For subjects not on dialysis at screening but requiring dialysis for the first time during the study, eGFR values after dialysis will be flagged.

Glomerular Filtration Rate will be estimated through creatinine clearance paediatric Schwartz (2009) formula and it will be available at each timepoint it is possible to derive it as depending on height and serum creatinine. Age at each timepoint from Central Laboratory file will be used. If not available, age from CRF data at the same visit will be used, and in case of missing data, imputation will be done as follows:

- If visit date is missing, age will be left as missing, so eGFR will not be calculated
- If visit date is available, then calculate the duration in days between the last visit with an available age and the visit with a missing age (visit y date visit x date + 1), and if this duration <= 365 days then imputed age will be the age at the previous visit, else impute with age (years) at previous visit + 1.

Please refer to Table 11 for the formula to be used.

Table 11 eGFR formula by age and gender categories

Category	eGFR Formula	Unit
< 1 year	(0.45 * Height (cm))/ (serum creatinine (umol/L) * 0.01131)	mL/min/1.73m 
1 - <13 years	(0.55 * Height (cm))/ (serum creatinine (umol/L) * 0.01131)	$mL/min/1.73m^2$
Females 13-≤18 years	(0.55 * Height (cm))/ (serum creatinine (umol/L) * 0.01131)	$mL/min/1.73m^2$
Males 13-≤18 years	(0.70 * Height (cm))/ (serum creatinine (umol/L) * 0.01131)	$mL/min/1.73m^2$

## 4.9.4. Vital Signs and Physical Examinations

The actual value and change from baseline will be summarised for each vital signs (height, weight, BMI, resting blood pressure, resting heart rate and temperature) parameter at each time point by treatment group. The vital signs will also be summarised by age categories at randomisation within treatment group.

As the temperature can be taken using different modes (Oral, Otic or Axillary), then it will not be presented in the summary statistics when the mode at Week x is different from the mode at Baseline and then the change from baseline will not be derived in that case. All values will be presented in the listing.

So for the temperature, summary by mode will be presented.

By-subject listings of vital sign measurements will be presented in data listings.

For physical examination, shift table from baseline to each time point will be presented. All physical examination findings will be presented in a data listing.

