## 4.2.6. Subpopulations

The following subgroups will be considered:

- Age at randomisation: 0 to <2 year/ ≥2 year to <6 years/ ≥6 years to <12 years/ ≥12 years to ≤18 years
- Gender: Male/Female
- Region: Europe/Rest of the World/United States

Europe and Rest of the World maybe pooled under Non-US if Rest of the World represents a low number of subjects (e.g. less than 5% of the overall Safety Population).

In case of imbalance between treatment groups regarding baseline characteristics, other subgroup analyses may be performed.

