## 4.5.1. Demographics

Summary statistics will be provided for age at randomisation (years) as continuous and categorical variables (section 4.2.6; the 0 to <2 year category will be divided in two categories: 0 to <1 year and 1 to <2 year) and below), sex, race, ethnicity, region, baseline height (cm), baseline weight (kg), and baseline body mass index (BMI; kg/m²).

The following age categories will be considered:

- New borns (0-27 days)
- Infants and toddlers (28 days-23 months)
- Children (2-11 years)
- Adolescents (12-17 years)
- Adults (18-64 years)

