Table 14.4.8.3	Clinical Laboratories – Chemistry - Liver Enzymes: Shift Table from Baseline to each Post-Baseline Value by timepoint (Safety Population)
Table 14.4.8.4	Clinical Laboratories – Iron Status Parameters: Shift Table from Baseline to each Post-Baseline Value by timepoint (Safety Population)
Table 14.4.8.5	Clinical Laboratories – Vitamins: Shift Table from Baseline to each Post-Baseline Value by timepoint (Safety Population)
Table 14.4.8.6	Clinical Laboratories – Bone Markers: Shift Table from Baseline to each Post-Baseline Value by timepoint (Safety Population)
Table 14.4.9.1	Vital Signs: Actual Values and Changes over Time (Safety Population)
Table 14.4.9.2	Vital Signs: Actual Values and Changes over Time, by Age (Safety Population)
Table 14.4.10	Physical Examination (Safety Population)
Table 14.4.11	Concomitant Medications (Safety Population)
Table 14.4.12	Dialysis Type over Time (Safety Population)
Table 14.4.13	Subject Reported Palatability and Acceptability over Time (Safety Population)
	Population)
7.2. Data l	Population)  Listings to be Generated  Investigational Product(s) Received for PA21 Dosing (Safety
7.2. Data I Listing 16.1.6.1.A	Population)  Listings to be Generated  Investigational Product(s) Received for PA21 Dosing (Safety Population)  Investigational Product(s) Received for Phoslyra Dosing (Safety
7.2. Data land Listing 16.1.6.1.A Listing 16.1.6.1.B	Population)  Listings to be Generated  Investigational Product(s) Received for PA21 Dosing (Safety Population)  Investigational Product(s) Received for Phoslyra Dosing (Safety Population)  Listing of Patients Receiving Test Drug(s)/Investigational Product(s)
7.2. Data I Listing 16.1.6.1.A Listing 16.1.6.1.B Listing 16.1.6.2	Population)  Listings to be Generated  Investigational Product(s) Received for PA21 Dosing (Safety Population)  Investigational Product(s) Received for Phoslyra Dosing (Safety Population)  Listing of Patients Receiving Test Drug(s)/Investigational Product(s) From Specific Batches, Where More Than One Batch Was Used  Listing of Subjects Receiving Study Drug Different than the One

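### Height, weight and BMI are tabulated only as raw values and raw changes, which show impaired growth poorly although growth deficiency is an event of special interest

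*SAP*

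**What the plan says.** Section 4.9.4 of the SAP states that the actual value and "change from baseline will be summarised for each vital signs (height, weight, BMI", with blood pressure, heart rate and temperature listed after them. It does this at each time point by treatment group and then adds: "The vital signs will also be summarised by age categories at randomisation within treatment group". Section 7.1 carries this through as Table 14.4.9.1 (overall) and Table 14.4.9.2, titled "Vital Signs: Actual Values and Changes over Time, by Age (Safety Population".

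The bands in Section 4.2.6 are "Age at randomisation: 0 to <2 year/ ≥2 year to <6 years/ ≥6 years to <12 years/ ≥12 years to ≤18 years", with no split by sex. Baseline anthropometry in Section 4.5.1 is raw as well: "baseline height (cm), baseline weight (kg), and baseline body mass index (BMI; kg/m²".

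The SAP defines no standard deviation score, percentile, growth velocity or growth reference. CDC is in the abbreviation list but is used nowhere else.

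Growth appears in two other places. Section 1.1 ends its list of the complications most relevant to children with "cardiovascular disease and growth failure". Table 8 in Section 4.9.1 makes this an event of special interest: "Events, which could be linked to (deficiencies in) growth and skeletal development and review of bone markers".

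**The concern.** Children are expected to gain height and weight over a study of this length, at a pace that depends on age and sex. A mean change in cm or kg mixes that expected gain with any effect of disease or treatment. It will usually be positive whether or not the children kept pace with their peers.

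The other planned sources do not fill the gap. The Table 8 terms cover bone disorders, fractures and bone or calcium metabolism; none measures growth. Bone markers are excluded under 36 months unless available from routine care (footnote 6 to Table 3). Three of them (osteocalcin, fibroblast growth factor 23 and tartrate-resistant acid phosphatase 5b) get no shift tables because paediatric normal ranges are missing (Section 4.9.3). Measured height and weight are the direct growth data in the study, and they are reported on the scale that is hardest to interpret for this question.

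**Working it through.** The SAP gives no figure for growth, so there is none to reproduce. Its only design calculation, the power for serum phosphorus, does not bear on this point.

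**1. Time on treatment.** Stage 1 lasts up to 10 weeks, with transfer possible from Week 4; Stage 2 lasts 24 weeks (Section 2.1). Completers therefore have 4 + 24 = 28 to 10 + 24 = 34 weeks, or 28/52 = 0.538 to 34/52 = 0.654 year.

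**2. Expected raw height change.** The growth rates are assumptions, not SAP figures: 4 to 7 cm/year in younger children and 0 to 2 cm/year in late adolescents. Change = rate × time.

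| | 28 weeks | 34 weeks |
|---|---|---|
| Younger, 4 to 7 cm/year | 2.2 to 3.8 cm | 2.6 to 4.6 cm |
| Late adolescent, 0 to 2 cm/year | 0 to 1.1 cm | 0 to 1.3 cm |

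**3. What slowed growth looks like.** Suppose, for illustration, that a younger child grows at half the expected pace. The raw gain is 1.1 to 1.9 cm at 28 weeks and 1.3 to 2.3 cm at 34 weeks. It is still positive and is about equal to or larger than the normal gain of a late adolescent. The sign and size of a raw change do not separate the two without the value expected for age and sex.

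**4. Does the by-age table resolve this?** The bands are 2, 4, 6 and just over 6 years wide, and both sexes are pooled. The oldest runs from 12-year-olds to subjects who may have stopped growing. Each band narrows the age mix, but the summary stays in raw units with nothing to compare it against.

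**5. Can the control arm supply the comparison?** Let s be the SD of the raw change, which the SAP does not give. The between-arm difference detectable with 80% power at two-sided 0.05 is (1.960 + 0.842) × √(1/n₁ + 1/n₂) × s:
- 100 vs 30 (planned): 0.58 s
- 70 vs 21 (after 30% drop-out in both arms): 0.70 s
- 10 vs 3 (the Table 1 minimum for most age groups): 1.84 s, rough at this size

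Age and sex mix within a band adds to s. By band, the arm comparison is therefore weak.

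**6. Distortion from age mix between arms (illustrative only).** The contrast between the two rows in step 2 is 2.6 − 1.3 = 1.3 to 4.6 − 0 = 4.6 cm at 34 weeks. At 28 weeks it is 1.1 to 3.8 cm. If the arms differed by 20 percentage points in the share of younger children, the means would differ by 0.2 × contrast: about 0.3 to 0.9 cm at 34 weeks and 0.2 to 0.8 cm at 28 weeks. The SAP gives no reason to expect 20 points, since randomisation is stratified by age (Section 2.2).

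**7. Are the inputs available?** Table 2 schedules height and weight at screening, baseline and Weeks 4, 10, 14, 22 and 34. Sex and age are summarised in Section 4.5.1, and Table 11 already combines height, age and gender for eGFR. Date of birth is not mentioned. The fallback for a missing age in Section 4.9.3 works in whole years, but the 0 to 27 day category in Section 4.5.1 implies that age at randomisation is held more finely.

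**The case against.** Nothing in Section 4.9.4 is false or contradictory. Growth is not a study objective or a named endpoint, and the comparison with Phoslyra is meant to be descriptive. Section 1.1 names growth failure as a complication of the disease, not as a suspected drug effect; only Table 8 makes it a safety topic. All of that stands and keeps the point small.

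Three stronger readings are tempting, and the document does not support them:
- *The plan ignores age.* It does not: the same section and Table 14.4.9.2 break the summaries down by age category.
- *The plan cannot detect slowed growth.* That is too absolute. There is a concurrent randomised arm, by-age tables, by-subject listings, bone markers and the special-interest category. A marked deficit could show in any of them.
- *Age mix will bias the arm comparison by a known amount.* Stratification by age is there to limit this. Some imbalance remains possible, because the oldest stratum runs from 9 to under 18 years, sex is not named as a stratum, and the Phoslyra arm is small. No particular size can be derived.

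It is also fair to say that standardised scores would not give the arm comparison much power with about 30 controls. Their main value is within arm: they show whether children kept pace with a reference, which raw change does not.

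**Conclusion.** The point holds as a cheap improvement. Height, weight and BMI are planned only as raw values and raw changes, in bands of 2 to about 6 years that pool the sexes. Those tables are poorly able to show impaired growth, although Table 8 makes growth deficiency an event of special interest and captures it with terms that do not measure growth. The primary endpoint is unaffected.

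The sizes above rest on assumed growth rates, an assumed halving of pace and 28 to 34 weeks of treatment; they illustrate the problem and do not estimate it. The feasibility of the fix rests on age being available more finely than in whole years.

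**What to change.** Keep Tables 14.4.9.1 and 14.4.9.2 as planned. Add height, weight and BMI standard deviation scores for age and sex, from one public growth reference named in the SAP.

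- **Summaries:** actual score and change from baseline at the scheduled visits and under the SAP's own End of Stage 1 and End of Stage 2 labels (Section 4.2.9), by treatment group, overall and by age group.
- **Main time point:** End of Stage 2. A fixed Visit 11 row would leave out subjects who enter Stage 2 early. End of Stage 1 may reflect as little as 4 weeks, or 0.3 to 0.5 cm at the assumed 4 to 7 cm/year.
- **Age at each visit:** age at randomisation plus elapsed days, not the whole-year fallback used for eGFR. Confirm first that age is held finely enough.
- **Coverage:** say how a subject outside the reference's age range is handled.
- **Age bands:** Section 4.2.6 (0 to <2, 2 to <6 years) and Section 5 (0 to <1, 1 to <6 years) differ for the younger children and must be reconciled before any by-age table is programmed.

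The cost is a lookup against a reference table and a few table rows, with no new data collection. The drawback is that one reference must serve several regions, which the report should state.
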